11.10.6 Special Notes on Response Assessment

- Target lesions that become “too small to measure” – While on study, all lesions (nodal and non-nodal) recorded at baseline should have their measurements recorded at each subsequent evaluation, even when very small (eg, 2 mm). However, sometimes lesions or lymph nodes which are recorded as target lesions at baseline become so faint on CT scan that the radiologist may not feel comfortable assigning an exact measure and may report them as being ‘too small to measure’. When this occurs, it is important that a value be recorded on the case report form. If it is the opinion of the radiologist that the non-lymph node lesion has likely disappeared, the measurement should be recorded as 0 mm. If the lesion is believed to be present and is faintly seen but too small to measure, a default value of 5 mm should be assigned (Note: It is less likely that this rule will be used for lymph nodes since they usually have a definable size when normal and are frequently surrounded by fat such as in the retroperitoneum; however, if a lymph node is believed to be present and is faintly seen but too small to measure, a default value of 5 mm should be assigned in this circumstance as well). This default value is derived from the 5 mm CT slice thickness (but should not be changed with varying CT slice

- thickness). The measurement of these lesions is potentially non-reproducible, therefore providing this default value will prevent false responses or progressions based upon measurement error. To reiterate, however, if the radiologist is able to provide an accurate measure, that should be recorded, even if it is below 5 mm.
- New lesions – The term “new lesion” always refers to the presence of a new finding that is definitely tumor. If a new lesion is identified via a modality other than CT or MRI, CT or MRI confirmation is recommended unless the new lesion is deemed unequivocally tumor. New findings that are not definitively tumor but may be benign (infection, inflammation, etc.) are not selected as new lesions, until that time when the review is certain they represent tumor.
 - If a new lesion is equivocal, for example because of its small size, continued therapy and follow-up evaluation will clarify if it represents truly new disease. If additional imaging confirms there is definitely a new lesion, then progression should be declared using the date of the initial scan.
 - A lesion identified on a follow-up study in an anatomical location that was not scanned at baseline is considered a new lesion and will indicate disease progression, regardless of any response that may be seen in target or non-target lesions present from baseline.
 - Any locoregional therapy not allowed per protocol
 - Any subject receiving locoregional therapy not allowed in the protocol while on study that directly affects one or more of the target lesions selected at baseline will be considered to be non-evaluable at all disease assessments that occur on or after the date of locoregional therapy with the exception of disease progression. However, if a lesion was completely resected where pathology was benign the subject will still be evaluable for response with 0 dimension reported.
 - If locoregional therapy was performed on a non-target lesion, that lesion will always be assessed as present unless pathology was benign.
 - Lesions that split or coalesce on treatment - When non-nodal lesions “fragment”, the longest diameters of the fragmented portions should be added together to calculate the target lesion sum and identified as a fragment of the original lesion. Similarly, as lesions coalesce, a plane between them may be maintained that would aid in obtaining maximal diameter measurements of each individual lesion. If the lesions have truly coalesced such that they are no longer separable, the vector of the longest diameter in this instance should be the maximal longest diameter for the “coalesced lesion”.
 - “Symptomatic deterioration” alone does not qualify as objective progression. If objective progression was not previously documented, then every effort should be made to document objective progression even after discontinuation of treatment.
 - In some circumstances it may be difficult to distinguish residual disease from scar or normal tissue. When the evaluation of CR depends on this determination, it is recommended that the residual lesion be further investigated by fine needle aspirate/biopsy, to confirm the CR status.
 - If a lesion disappears and reappears at a subsequent time point it should continue to be measured. However, the patient’s response at the point in time when the lesion reappears will depend upon the status of his/her other lesions. For example, if the patient’s tumor had reached a CR status and the lesion reappeared, then the patient would be considered PD at the time of reappearance. In contrast, if the tumor status was a partial response (PR) or SD and one lesion which had disappeared then

reappears, its maximal diameter should be added to the sum of the remaining lesions for a calculated response: in other words, the reappearance of an apparently 'disappeared' single lesion amongst many which remain is not in itself enough to qualify for PD: that requires the sum of all lesions to meet the PD criteria.

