CRS = cytokine release syndrome; CT = computed tomography; ECG = electrocardiogram; ECHO = echocardiogram; ECOG PS = Eastern Cooperative Oncology Group Performance Status; EOI = end of infusion; FT4 = free T4; HIV = human immunodeficiency virus; ICANS = immune effector cell-associated neurotoxicity syndrome; IV = intravenous; LDH = Lactate dehydrogenase; MUGA Scan = multigated acquisition scan; MRI = magnetic resonance imaging; NYHA = New York Heart Association; PK = pharmacokinetic; Q6W = every 6 weeks; Q12W = every 12 weeks; RECIST 1.1 = Response Evaluation Criteria in Solid Tumors 1.1; TSH = thyroid-stimulating hormone

^a All procedures and assessments on dosing days are to be completed prior to study drug administration unless otherwise indicated. Assessments should not be performed from the infusion line.

^b Each visit week and day is relative to day 1 of each cycle. Cycle 1 visits have a \pm 1-day window from designated time point unless otherwise specified.

- ^c Additional on-treatment pregnancy testing may be performed at the investigator's discretion if there is suspicion that a female subject is pregnant or per local laws and regulations.
- ^d **If screening local labs are obtained within 48 hours prior to cycle 1 day 1 dose, pre-infusion cycle 1 day 1 samples do not have to be repeated. Where applicable, cycle 1 day 8 and day 15 local labs must be obtained within 48 hours prior to dose (day 8 and day 15). Results must be reviewed prior to study drug administration.**
- ^e **If screening local labs are obtained within 72 hours prior to cycle 1 day 1 dose, the pre-infusion cycle 1 day 1 samples do not have to be repeated. Results must be reviewed prior to study drug administration.**
- ^f Imaging assessments must be within 21 days prior to the first dose of tarlatamab.
- ^g Timing is based on first dose of tarlatamab (C1D1).

Table 1-2. Schedule of Activities: Cycle 2+

Procedure ^a	Treatment Period ^b				EOT ^c	SFU ^d	LTFU ^{e,f}	As clinically indicated	Notes
	Cycle 2		Cycle 3+						
Day	1	15	1	15					
GENERAL AND SAFETY ASSESSMENTS									
Physical examination (including neurological exam)	[X]	X	[X]	X	X	X		X	Physical exam must be completed prior to start of infusion on treatment days. [X]: Must include weight on Day 1 of every cycle.
Vital Signs	X	X	X	X	X	X		X	Includes systolic/diastolic blood pressure, heart rate, respiratory rate, pulse oximetry, and temperature
ECOG PS	X		X		X	X			
ECG					X			X	
Adverse events	continuous							X	

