Subjects with chronic hepatitis B virus (HBV) infection inactive carrier state, defined as presence of HBV surface antigen [HBsAg-positive] and HBV DNA viral load below the limit of quantification [HBV DNA negative], are allowed with a requirement for regular monitoring for reactivation for the duration of treatment on the study and assessing the need for HBV prophylaxis therapy per local or institutional guidelines.

213 Major surgery within 28 days of first dose tarlatamab.

Prior/Concomitant Therapy

214 **Currently or previously enrolled in a tarlatamab study.**

215 Prior therapy with any selective inhibitor of the DLL3 pathway.

216 Prior anti-cancer therapy within 21 days prior to first dose of study treatment.

Exceptions:

- Subjects who received conventional chemotherapy are eligible if at least 14 days have elapsed and if all treatment-related toxicity has been resolved to grade ≤ 1 or to levels dictated in the eligibility criteria, before first dose of study treatment, with the exception of alopecia or toxicities considered irreversible (defined as having been present and stable for > 30 days) which are not otherwise described in the exclusion criteria.
- Prior palliative radiotherapy must have been completed at least 7 days before the first dose of tarlatamab.

217 Receiving systemic steroid therapy or any other form of immunosuppressive therapy within 7 days prior to the first dose of tarlatamab.

- Prophylactic dexamethasone required by the protocol and any anti-emetic therapies are allowed
- Low-dose corticosteroids (prednisone ≤ 10 mg per day or equivalent is permitted during the trial)

218 Treatment with live virus, including live-attenuated vaccination, within 14 days prior to the first dose of tarlatamab. Inactive vaccines (eg, non-live or non-replicating agent) and live viral non-replicating vaccines (eg, Jynneos for mpox infection) within 3 days prior to first dose of tarlatamab.

Prior/Concurrent Clinical Study Experience

219 Currently receiving treatment in another investigational device or drug study, or less than 30 days since ending treatment on another investigational device or drug study(ies). Other investigational procedures while participating in this study are excluded.

Other Exclusions

220 Female subjects of childbearing potential unwilling to use protocol-specified method of contraception (see [Section 11.5](#)) during treatment and for an additional **60** days after the last dose of tarlatamab.

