6.1.6 Excluded Treatments, Medical Devices, and/or Procedures During Study Period

The following treatments and/or procedures are excluded within the timeframes specified during the study:

- Other investigational agents, devices (other than those specified in the protocol) and procedures are prohibited while on study treatment.
- Anticancer therapies other than those specified in the protocol are prohibited while on study treatment.
- Radiation therapy
 - Exception: Radiation therapy for symptom control (eg, bone metastasis) or brain metastasis treatment may be allowed after discussion with the medical monitor. The radiation therapy should not include the thoracic field and must have been completed at least 7 days before the subsequent dose of tarlatamab.
- Immunosuppressive agents with the exception of those required by protocol, treatment for adverse events, CNS metastases, corticosteroid replacement therapy, or unless agreed upon by the investigator and medical monitor.
- During tarlatamab treatment: Live and live-attenuated vaccines are prohibited for the duration of tarlatamab treatment.
 - Live viral non-replicating vaccine (eg, Jynneos for mpox infection) is allowed when administered > 3 days before or > 3 days after a tarlatamab infusion.
 - Seasonal influenza vaccines for injection are generally killed virus vaccines and are allowed when administered > 3 days before or > 3 days after a tarlatamab infusion. However, intranasal influenza vaccines (eg, Flu - Mist®) are live-attenuated vaccines, and are not allowed at any time during tarlatamab treatment.
 - Vaccinations for coronavirus disease 2019 ([COVID-19], severe acute respiratory syndrome coronavirus 2 [SARS-CoV-2] vaccination) are generally not live or live-attenuated and are allowed when administered > 3 days before or > 3 days after a tarlatamab infusion.
 - After completion of tarlatamab treatment: live and live-attenuated vaccines are prohibited for a further **60** (+5) days after the last dose of tarlatamab.
- Subjects must not schedule any major elective surgery during the treatment period and for at least 30 days after the last administration of study treatment. If a subject undergoes any unexpected surgery during the course of the study, all study

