treatments must be withheld, and the investigator or designee should notify the sponsor's medical monitor as soon as possible. A subject may be allowed to resume study drugs if both the investigator and sponsor's medical monitor agree to restart study therapy.

6.1.7 Continuation on Investigational Product Treatment After First Radiologic Disease Progression

This section details the conditions necessary to allow continued study treatment after first disease progression in subjects that, in the investigator's judgment, continue to have clinical benefit. All of the following criteria must be met:

- Subject continues to have clinical benefit per the investigator's judgment.
- Subject has stable ECOG PS.
- Absence of threat to vital organs or critical anatomical sites (eg, respiratory failure due to tumor compression, spinal cord compression) requiring urgent alternative medical intervention with persistent immediate threat to vital organs after intervention. The presence of brain metastases is allowed provided the lesions are amenable to radiation therapy or dexamethasone (or corticosteroid equivalent), and the subject is clinically stable in the investigator's judgment.
- Subject continues to tolerate study drug.
- No other treatment discontinuation criteria are met ([Table 6-2](#) and **Section 11.7.1**).
- No significant, unacceptable, or irreversible toxicities related to any dose of the study treatment or treatment-related adverse events of Common Terminology Criteria for Adverse Events (CTCAE) grade 3 at the current dose at the time of progression.
- Radiation therapy is permitted after discussion with the medical monitor. Palliative radiation and/or surgery for new, progressive, or symptomatic lesions is permitted. Study treatment must be held during either treatment (radiation and/or surgery) and the treatment must be completed at least 7 days before the subsequent dose of study treatment.

Subjects should continue to perform all protocol-required procedures as noted in the Schedule of Activities (Section [1.3](#); imaging, labs, and clinic visits).

Any subsequent (investigator determined) progressive disease per RECIST 1.1 from a new baseline set at initial progression will result in permanent discontinuation of study treatment.

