8.3 Efficacy Assessments

8.3.1 Radiological Imaging Assessment

The extent of disease will be evaluated by contrast-enhanced computed tomography (CT)/magnetic resonance imaging (MRI) according to RECIST 1.1 (Section 11.10). All radiological imaging will be performed as indicated in the Site Imaging Manual provided by the central imaging core laboratory. In order to reduce radiation exposure for subjects, low dose CT should be utilized whenever possible.

Screening scans:

The screening scans must be performed within 21 days prior to enrollment. If there are multiple screening scans, the one closest to the enrollment will be used as baseline. Assessments that were performed as SOC prior to signature of informed consent, but within 21 days prior to first dose of tarlatamab can be used as screening assessments and do not need to be repeated to confirm subject eligibility.

Radiological assessment must include CT/MRI of the chest, abdomen, and pelvis, as well as assessment of all other known sites of disease (as detailed within the Site Imaging Manual).

All subjects must have imaging of the brain performed within 21 days prior to the first dose of tarlatamab. All brain scans for subjects are required to be MRI unless MRI is contraindicated, and then CT with contrast is acceptable.

Subsequent scans:

All subsequent scans should be performed in the same manner (eg, with the same contrast, MRI field strength) as at screening preferably on the same scanner. If the imaging modality must be altered (eg, unscheduled assessment), consultation with the medical monitor is recommended.

Subsequent brain MRI/CT scans may be performed at any time, if in the judgement of the managing physician, the subject displays signs, or symptoms of CNS metastasis.

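### Radiotherapy that the protocol permits to a target lesion does not make later scans non-evaluable, and a baseline scan can predate the last chemotherapy, so shrinkage from other treatment can count toward the primary ORR

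*Protocol*

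**What the plan says.** **Local therapy on study.** Protocol 11.10.6 applies its non-evaluable rule to "Any subject receiving locoregional therapy not allowed in the protocol while on study that directly affects one or more of the target lesions". Later assessments are then non-evaluable, except that progression still counts. Under the same bullet: "If locoregional therapy was performed on a non-target lesion, that lesion will always be assessed as present unless pathology was benign".

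Protocol 6.1.6 lists radiotherapy as excluded, with an exception: "Radiation therapy for symptom control (eg, bone metastasis) or brain metastasis treatment may be allowed after discussion with the medical monitor". The limit on location is "The radiation therapy should not include the thoracic field", and the radiotherapy must be finished at least 7 days before the next tarlatamab dose. Nothing is said about target lesions.

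**When assessment stops.** Under Protocol 11.10.5 and SAP 5.2, BOR uses scans taken before subsequent anticancer treatment. SAP Appendix C censors PFS at new anti-cancer therapy, and SAP 5.2 applies the same rules to DOR. Neither document says whether radiotherapy permitted under 6.1.6 falls under either term.

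**Baseline.** Table 1-1, footnote f: "Imaging assessments must be within 21 days prior to the first dose of tarlatamab". Protocol 8.3.1 adds: "If there are multiple screening scans, the one closest to the enrollment will be used as baseline". Exclusion 216 sets a general 21-day washout, shortened to 14 days for conventional chemotherapy, and for radiotherapy: "Prior palliative radiotherapy must have been completed at least 7 days before the first dose of tarlatamab". No section requires the baseline scan to follow the last prior treatment.

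**The concern.** Section 11.10.6 accepts that local treatment of a target lesion confounds the response assessment. That reasoning does not depend on whether the treatment was permitted, since a lesion shrinks under radiation either way. By limiting the rule to non-permitted therapy, the protocol leaves the permitted case without any rule.

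The baseline question is the same problem at the other end of the measurement. A partial response is a fall of at least 30% from the baseline sum of diameters (Protocol 11.10.4). If chemotherapy was given after the baseline scan, part of the fall may belong to the chemotherapy.

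With no control arm, every RECIST response is read as a tarlatamab effect. The only planned ORR sensitivity analysis (SAP 6.7.1 and 9.5.1) restricts to subjects with measurable baseline disease by central review. It addresses neither problem.

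**Working it through.** **1. Can a target lesion be irradiated under 6.1.6 and stay evaluable?** The exception names bone metastasis as an example. Section 11.10.1.2.4 allows a bone lesion with a measurable soft-tissue component to be measurable, hence a target lesion. Abdominal and pelvic lesions are also outside the thoracic field. The 11.10.6 rule does not apply, because the therapy is permitted. The stopping rule for BOR is undefined on the point. One indirect pointer is that Protocol 4.1 ends study treatment at the start of new anticancer therapy, whereas 6.1.6 provides for a further tarlatamab dose after permitted radiotherapy. That suggests such radiotherapy is not meant as new anticancer therapy, but it is not a definition.

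**2. How much must one treated lesion shrink?** Assume k target lesions of equal size, with the others unchanged. The treated lesion is 1/k of the sum, so it must shrink by 30% × k:

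- k = 1: 30%
- k = 2: 60%
- k = 3: 90%
- k = 4 or 5: more than 100%, so impossible from that lesion alone

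The effect needs few target lesions, a dominant treated lesion, or other lesions that have already shrunk part of the way.

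**3. Gap between baseline scan and last prior therapy.** Maximum gap = 21-day scan window minus washout.

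| Prior therapy | Washout (days) | Maximum gap (days) |
|---|---|---|
| Conventional chemotherapy | 14 | 21 − 14 = 7 |
| Palliative radiotherapy | 7 | 21 − 7 = 14 |
| Other anticancer therapy | 21 | 21 − 21 = 0 |

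The radiotherapy row is mostly closed by Protocol 11.10.1.2.6, under which a previously irradiated lesion is not measurable unless measurable progression was shown before enrollment. The text does not say that this progression must follow the irradiation. A lesion that progressed, was scanned and was then irradiated before first dose can meet the exception as worded. The chemotherapy row has no such safeguard.

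**4. The plan's own figures.** Protocol Table 9-1 (n = 30) is reproduced by P(X ≥ r) with X ~ Bin(30, p), r = 8 for above 25% and r = 10 for above 30%. At p = 0.35 this gives 87.6% and 64.2% (stated 88%, 64%). At p = 0.40 it gives 95.6% and 82.4% (stated 96%, 82%). The sample-size arithmetic is correct.

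**5. What a few misattributed responses would do.** The documents give no count, so m = 0 to 3 is an assumption. Fix m subjects as responders and let the other 30 − m respond at the true rate: P(Y ≥ r − m), with Y ~ Bin(30 − m, p).

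| True ORR | m | P(observed > 25%) | P(observed > 30%) |
|---|---|---|---|
| 0.35 | 0 | 87.6% | 64.2% |
| 0.35 | 1 | 92.6% | 73.5% |
| 0.35 | 2 | 96.1% | 81.8% |
| 0.35 | 3 | 98.2% | 88.5% |
| 0.40 | 0 | 95.6% | 82.4% |

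Two such subjects make a true 0.35 look almost the same as the table's 0.40 row. On the observed scale, a subject who would otherwise be a non-responder adds 1/30 = 3.3 points. For example, 12/30 is 40.0% (Clopper-Pearson 95% CI 22.7 to 59.4), and without two of those responses 10/30 is 33.3% (17.3 to 52.8). Allowing that affected subjects might have responded anyway, the expected shift at 0.35 with m = 2 is 2 × 0.65/30 = 4.3 points.

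**The case against.** The case against is that the routes are narrow and partly guarded, and much of it stands.

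- **Narrow routes.** Section 6.1.6 requires discussion with the medical monitor and excludes the thorax. Bone lesions without a soft-tissue component are not measurable. Treating one lesion often cannot move the whole sum by 30%. The chemotherapy gap is at most 7 days, in subjects who have already progressed after at least two lines, and the closest of several screening scans is used.
- **Confirmation.** Responses must be confirmed at least 4 weeks later. That tests persistence, not cause. Keeping a treated non-target lesion as present blocks a complete response but not a partial one.
- **Radiotherapy or surgery after progression.** Section 6.1.7 states "Palliative radiation and/or surgery for new, progressive, or symptomatic lesions is permitted", and a reader might infer that this inflates DOR and PFS too. The documents do not support that. Section 6.1.7 applies only after first progression, and by the same assessor DOR and PFS have ended by then (SAP 5.2, Appendix C). This point does not rest on 6.1.7.
- **Radiotherapy before first dose.** A reader might take the 14-day figure as an open gap. It is not, because 11.10.1.2.6 and 11.10.1.3 cover most such lesions. Only the order of progression and irradiation is left unstated.
- **Separate CRF entries.** SAP 5.1 names on-study radiotherapy apart from subsequent anticancer therapies, which might be read as proof that radiotherapy does not end BOR. That list only supplies dates for last known alive. The documents are silent on the question.

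What remains is an unguarded case under 6.1.6 and a short chemotherapy gap, both acting in the direction of a higher ORR.

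**Conclusion.** The point holds in limited form. As written, the response rules can credit shrinkage from permitted radiotherapy, or from chemotherapy given after the baseline scan, to tarlatamab in the primary ORR. It would go too far to say that ORR is inflated, or inflated by a given amount. The documents contain no rate for either event and the number of affected subjects may be zero. The only firm size is 3.3 points per subject wrongly counted as a responder, and the m = 1 to 3 results are illustrations. Even a shift of two responses lies well inside the 95% interval for 12/30, and no hypothesis is tested. The change is still worth making because the effect runs in one direction, no control arm offsets it, and it can be removed by wording.

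**What to change.** 1. In Protocol 11.10.6, delete the qualifier that limits the target-lesion rule to therapy the protocol does not allow, and the matching words in the bullet heading. Assessments after any on-study local therapy to a target lesion would then be non-evaluable except for progression. Mirror this in SAP 5.2 and Appendix B.
2. State in the SAP whether on-study radiotherapy counts as new anticancer therapy for BOR, DOR and PFS. A yes would reach further than item 1, since it would also stop BOR after radiotherapy to a non-target lesion.
3. Flag subjects whose baseline scan predates their last prior anticancer therapy, and add an ORR sensitivity analysis counting them as non-responders. A repeat scan need not be required, as that would add imaging for some subjects.

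**Cost.** Protocol and SAP wording, one data flag and one extra table. ORR may be slightly lower. A response not yet confirmed when a target lesion is treated could no longer be confirmed, and the subject stays in the denominator. Some DOR and PFS times would be censored earlier, possibly informatively. The SAP should therefore also say whether such non-evaluable scans count as missed under the last row of Appendix C.

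None of this bears on whether radiotherapy may be given.
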